**Note: Statistical comparison of PK parameter Tmax (CPStat2) will have the following format:**

Page 1 of X

Table Statistical Comparison of Plasma Nicotine Pharmacokinetic Parameter Tmax (PK Population)

Parameter	Difference <X> - <Y>		
	Median	90% Confidence Interval	p-value
Tmax	X.XX	-X.XXXX - X.XXXX	X.XXXX

Product: <Label for First Product>  
 Product: <Label for Second Product>

---

**Notes for Generating the Actual Table:**

**Presentation of Data:**

- Median difference will be presented to 2 decimals or 3 significant figures
- 90% CI will be presented to 4 decimals
- p-value will be presented to 4 decimals

**Programmers Note:**

The comparisons will be: P1R vs CIG and P1M vs CIG, where P1R = THS regular stick; P1M = THS menthol stick; and CIG = Combustible cigarette.  
 Add column identifying the comparisons.

The difference between products (product effect) and the 95% confidence interval for the difference was calculated using Hodges-Lehmann estimator.

Program: DM\_PX:[HLXXXXX.PKSAS]XXXX.SAS DDMMYYYY HH:MM

Philip Morris Products S.A.  
 THS Induction device and regular or menthol sticks, P1-PK-12  
 [REDACTED] CA39924

**Note: Summary table (CPD1) will have the following format:**

Table CPD1 Summary of VAS Craving Assessment by Study Product and Time Point (PK Population)

Time Point	Sex	Statistic	Product		
			P1R	P1M	CIG
XXXXXXXXXXXXXX	Female	n	X	X	X
		Mean	X.X	X.X	X.X
		SD	X.XX	X.XX	X.XX
		CV (%)	XX.X	XX.X	XX.X
		SEM	X.XX	X.XX	X.XX
		Minimum	XX	XX	XX
		1st quartile	X.X	X.X	X.X
		Median	X.X	X.X	X.X
		3rd quartile	X.X	X.X	X.X
		Maximum	XX	XX	XX
		95% CI	X.X-X.X	X.X-X.X	X.X-X.X
XXXXXXXXXXXXXX	Male	n	X	X	X
		Mean	X.X	X.X	X.X
		SD	X.XX	X.XX	X.XX
		CV (%)	XX.X	XX.X	XX.X
		SEM	X.XX	X.XX	X.XX
		Minimum	XX	XX	XX
		1st quartile	X.X	X.X	X.X
		Median	X.X	X.X	X.X
		3rd quartile	X.X	X.X	X.X
		Maximum	XX	XX	XX
		95% CI	X.X-X.X	X.X-X.X	X.X-X.X

P1R: < >

P1M: < >

CIG: < >

Program: /CAXXXX/sas\_prg/pksas/PROGRAMNAME.SAS DDMMYYYY HH:MM

Programmer Note: All collection time points and overall (sex combined) for each timepoint will also be presented in the table.

Philip Morris Products S.A.

THS Induction device and regular or menthol sticks, P1-PK-12

CA39924

Page 1 of X

Table CAEO Overall Product Use Emergent Adverse Event Frequency by Study Product – Number of Subjects Reporting the Event  
(% of Subjects Used Study Product) (Safety Population)

Adverse Event	Product Administration					
	Admission (N = X)	P1R (N = X)	P1M (N = X)	CIG (N = X)	Overall (N = X)	SFU (N = X)
Number of Subjects With PUEAEs	X ( X%)	X ( XX%)	X ( XX%)	X ( X%)	X ( XX%)	X ( XX%)
Number of Subjects With SAEs	X ( X%)	X ( XX%)	X ( XX%)	X ( X%)	X ( XX%)	X ( XX%)
Number of Subjects With IP Events	X ( X%)	X ( XX%)	X ( XX%)	X ( X%)	X ( XX%)	X ( XX%)
Number of Subjects With AEs Leading to Discontinuation	X ( X%)	X ( XX%)	X ( XX%)	X ( X%)	X ( XX%)	X ( XX%)
Number of Subjects With AEs Leading to Death	X ( X%)	X ( XX%)	X ( XX%)	X ( X%)	X ( XX%)	X ( XX%)
Number of Subjects With AEs Related to IP	X ( X%)	X ( XX%)	X ( XX%)	X ( X%)	X ( XX%)	X ( XX%)

P1R: < >

P1M: < >

CIG: < >

Although a subject may have had 2 or more adverse events, the subject is counted only once within a category. The same subject may appear in different categories.

PUEAEs = Product use-emergent adverse events; SAEs = Serious adverse events; IP = Investigational product

Admission = after ICF and prior to the product test on Day 1

SFU = after discharge from CRU to safety follow-up visit

Program: /CAXXXX/sas\_prg/stsas/tab/programname2022Q1.sas DDMMYYYY HH:MM

Philip Morris Products S.A.

THS Induction device and regular or menthol sticks, P1-PK-12

CA39924

Page 1 of X

Table CAES Product Use Emergent Adverse Event Frequency by Study Product - Number of Subjects Reporting the Event  
(% of Subjects Used Study Product) (Safety Population)

Adverse Event	Product Administration					
	Admission (N = X)	P1R (N = X)	P1M (N = X)	CIG (N = X)	Overall (N = X)	SFU (N = X)
Number of Subjects With PUEAEs	X ( X%)	X ( XX%)	X ( XX%)	X ( X%)	X ( XX%)	X ( XX%)
Number of Subjects Without PUEAEs	XX ( XX%)	XX ( XX%)	XX ( XX%)	XX ( XX%)	XX ( XX%)	XX ( XX%)
Eye disorders	X ( X%)	X ( X%)	X ( X%)	X ( X%)	X ( X%)	X ( X%)
Vision blurred	X ( X%)	X ( X%)	X ( X%)	X ( X%)	X ( X%)	X ( X%)
Gastrointestinal disorders	X ( X%)	X ( X%)	X ( X%)	X ( X%)	X ( X%)	X ( X%)
Dyspepsia	X ( X%)	X ( X%)	X ( X%)	X ( X%)	X ( X%)	X ( X%)
Nausea	X ( X%)	X ( X%)	X ( X%)	X ( X%)	X ( X%)	X ( X%)
Musculoskeletal and connective tissue disorders	X ( X%)	X ( X%)	X ( X%)	X ( X%)	X ( X%)	X ( X%)
Back pain	X ( X%)	X ( X%)	X ( X%)	X ( X%)	X ( X%)	X ( X%)
Muscle cramps	X ( X%)	X ( X%)	X ( X%)	X ( X%)	X ( X%)	X ( X%)
Musculoskeletal pain	X ( X%)	X ( X%)	X ( X%)	X ( X%)	X ( X%)	X ( X%)
Nervous system disorders	X ( X%)	X ( X%)	X ( X%)	X ( X%)	X ( X%)	X ( X%)
Headache	X ( X%)	X ( X%)	X ( X%)	X ( X%)	X ( X%)	X ( X%)
Reproductive system and breast disorders	X ( X%)	X ( X%)	X ( X%)	X ( X%)	X ( X%)	X ( X%)
Vaginal discharge	X ( X%)	X ( X%)	X ( X%)	X ( X%)	X ( X%)	X ( X%)
Respiratory, thoracic and mediastinal disorders	X ( X%)	X ( X%)	X ( X%)	X ( X%)	X ( X%)	X ( X%)
Epistaxis	X ( X%)	X ( X%)	X ( X%)	X ( X%)	X ( X%)	X ( X%)

P1R: < >

P1M: < >

CIG: < >

Although a subject may have had 2 or more adverse events, the subject is counted only once within a category. The same subject may appear in different categories.

Adverse events are classified according to MedDRA Version 25.1.

PUEAEs = Product use-emergent adverse events

Admission = after ICF and prior to the product test on Day 1

SFU = after discharge from CRU to safety follow-up visit

Program: /CAXXXX/sas\_prg/stsas/tab/programname2022Q1.sas DDMMYY HH:MM

Philip Morris Products S.A.

THS Induction device and regular or menthol sticks, P1-PK-12

CA39924

Page 1 of X

Table CAEE Product Use Emergent Adverse Event Frequency by Study Product – Number of Adverse Events  
(% of Total Adverse Events) (Safety Population)

Adverse Event	Product Administration					
	Admission (N = X)	P1R (N = X)	P1M (N = X)	CIG (N = X)	Overall (N = X)	SFU (N = X)
Number of PUEAEs	X ( X%)	X ( XX%)	X ( XX%)	X ( X%)	X ( XX%)	X ( XX%)
Eye disorders	X ( X%)	X ( X%)	X ( X%)	X ( X%)	X ( X%)	X ( X%)
Vision blurred	X ( X%)	X ( X%)	X ( X%)	X ( X%)	X ( X%)	X ( X%)
Gastrointestinal disorders	X ( X%)	X ( X%)	X ( X%)	X ( X%)	X ( X%)	X ( X%)
Dyspepsia	X ( X%)	X ( X%)	X ( X%)	X ( X%)	X ( X%)	X ( X%)
Nausea	X ( X%)	X ( X%)	X ( X%)	X ( X%)	X ( X%)	X ( X%)
Musculoskeletal and connective tissue disorders	X ( X%)	X ( X%)	X ( X%)	X ( X%)	X ( X%)	X ( X%)
Back pain	X ( X%)	X ( X%)	X ( X%)	X ( X%)	X ( X%)	X ( X%)
Muscle cramps	X ( X%)	X ( X%)	X ( X%)	X ( X%)	X ( X%)	X ( X%)
Musculoskeletal pain	X ( X%)	X ( X%)	X ( X%)	X ( X%)	X ( X%)	X ( X%)
Nervous system disorders	X ( X%)	X ( X%)	X ( X%)	X ( X%)	X ( X%)	X ( X%)
Headache	X ( X%)	X ( X%)	X ( X%)	X ( X%)	X ( X%)	X ( X%)
Reproductive system and breast disorders	X ( X%)	X ( X%)	X ( X%)	X ( X%)	X ( X%)	X ( X%)
Vaginal discharge	X ( X%)	X ( X%)	X ( X%)	X ( X%)	X ( X%)	X ( X%)
Respiratory, thoracic and mediastinal disorders	X ( X%)	X ( X%)	X ( X%)	X ( X%)	X ( X%)	X ( X%)
Epistaxis	X ( X%)	X ( X%)	X ( X%)	X ( X%)	X ( X%)	X ( X%)

P1R: < >

P1M: < >

CIG: < >

Adverse events are classified according to MedDRA Version 25.1.

PUEAEs = Product use-emergent adverse events

Admission = after ICF and prior to the product test on Day 1

SFU = after discharge from CRU to safety follow-up visit

Program: /CAXXXX/sas\_prg/stsas/tab/programname2022Q1.sas DDMMYYYY HH:MM

Philip Morris Products S.A.

THS Induction device and regular or menthol sticks, P1-PK-12

CA39924

Page 1 of X

Table CAESR Product Use Emergent Adverse Event Frequency by Study Product, Severity, and Relationship to Study Product –  
Number of Adverse Events (Safety Population)

Adverse Event	Product	Number of Subjects With PUEAEs		Severity			Relationship to Study Product		Relationship to Study Procedure	
		PUEAEs	PUEAEs	Mild	Moderate	Severe	Unrelated	Related	Unrelated	Related
Abdominal pain	XXX	X	X	X	X	X	X	X	X	X
Constipation	XXX	X	X	X	X	X	X	X	X	X
Dry throat	XXX	X	X	X	X	X	X	X	X	X
Dysmenorrhoea	XXX	X	X	X	X	X	X	X	X	X
Dyspepsia	XXX	X	X	X	X	X	X	X	X	X
Headache	XXX	X	X	X	X	X	X	X	X	X
	XXX	X	X	X	X	X	X	X	X	X
Myalgia	XXX	X	X	X	X	X	X	X	X	X
Nasal congestion	XXX	X	X	X	X	X	X	X	X	X
Skin laceration	XXX	X	X	X	X	X	X	X	X	X
<hr/>										
Admission		X	X	X	X	X	X	X	X	X
P1R		X	X	X	X	X	X	X	X	X
P1M		X	X	X	X	X	X	X	X	X
CIG		X	X	X	X	X	X	X	X	X
Overall		X	X	X	X	X	X	X	X	X
FU		X	X	X	X	X	X	X	X	X
<hr/>										

P1R: < >

P1M: < >

CIG: < >

Adverse events are classified according to MedDRA Version 25.1.

PUEAEs = Product use-emergent adverse events

Admission = after ICF and prior to the product test on Day 1

SFU = after discharge from CRU to safety follow-up visit

Overall = From the product use on Day 1 through the discharge from CRU.

Program: /CAXXXX/sas\_prg/stsas/tab/programname2022Q1.sas DDMMYY HH:MM

Philip Morris Products S.A.

THS Induction device and regular or menthol sticks, P1-PK-12

CA39924

---

Page 1 of X

Table 14.3.2.1 Serious Adverse Events (Safety Population)

---

Will match format of Appendix 16.2.7

Or contain statement as follows:

"There were no events that met this criteria."

Program: /CAXXXX/sas\_prg/stsas/tab/programname2022Q1.sas DDMMYYYY HH:MM

Philip Morris Products S.A.  
 THS Induction device and regular or menthol sticks, P1-PK-12  
 [REDACTED] CA39924

Page 1 of X

Table CLBO Out-of-Range Values and Recheck Results - <Clinical Laboratory Panel> (Safety Population)

Subject Number	Age/ Sex	Study Period	Day	Hour	Date	Time	Parameter1 <Range> (Unit)	Parameter2 <Range> (Unit)	Parameter3 <Range> (Unit)	Parameter4 <Range> (Unit)
X 1	XX/X	Screen			DDMMYYYY	HH:MM:SS	XX HN XX LN	XX LY-	XX LN G1	XX HN XX LN
			-X	-X.XX	DDMMYYYY	HH:MM:SS				

Programmer Note: Replace Parameter1, 2 etc. with actual lab tests in the study. Sort unscheduled assessment and early termination chronologically with other scheduled assessments and rechecks. Recheck should be sorted with the scheduled time point the recheck is for. Unscheduled and Early Termination records should only be included if they are out of range or recheck results.

F = Female; M = Male

H = Above reference range; L = Below reference range

CS Flag: N = Not clinically significant; Y = Clinically significant

PI interpretation: - = Not clinically significant

CTCAE grade (Version 5.0): G1 = Mild

Program: /CAXXXX/sas\_prg/stsas/tab/programname2022Q1.sas DDMMYYYY HH:MM

Philip Morris Products S.A.  
 THS Induction device and regular or menthol sticks, P1-PK-12  
 [REDACTED] CA39924

Page 1 of X

Table CLBS Clinically Significant Laboratory and Corresponding Results (Safety Population)

Subject Number	Age/ Study Period	Day	Hour	Date	Time	Department	Test	Result	Reference Range	Unit
X XX/X 1		X	-X.X	DDMMYYYY	HH:MM	Serum Chemistry	Cholesterol	XXX	X - X	mg/dL

Programmer Note: All time points for a subject/test with at least one value deemed as CS by the PI will be presented in this table.

H = Above reference range

Computer: Y = Clinically significant

PI Interpretation: R = Recheck requested, + = Clinically significant

If no event meet this criteria then include a statement as follows:

"There were no clinical laboratory results documented as clinically significant by the PI."

Philip Morris Products S.A.

THS Induction device and regular or menthol sticks, P1-PK-12

CA39924

Page 1 of X

Table CLBD Clinical Laboratory Summary and Change From Baseline - <Clinical Laboratory Panel> (Safety Population)

Laboratory Test (units)	Reference Range	Time Point	Statistic	Randomized Product Sequence					
				XXX (N = X)	XXX (N = X)	XXX (N = X)	XXX (N = X)	XXX (N = X)	XXX (N = X)
Testname (unit)	< - >#	Baseline	n	X	X	X	X	X	X
			Mean	X.X*	X.X	X.X	X.X	X.X	X.X*
			SD	X.XX	X.XX	X.XX	X.XX	X.XX	X.XX
			Minimum	XX	XX	XX	XX	XX	XX
			Median	X.X	X.X	X.X	X.X	X.X	X.X
			Maximum	XX	XX	XX	XX	XX	XX
		Discharge	Absolute	n	X	X	X	X	X
			Mean	X.X^	X.X	X.X	X.X^	X.X	X.X
			SD	X.XX	X.XX	X.XX	X.XX	X.XX	X.XX
			Minimum	XX	XX	XX	XX	XX	XX
			Median	X.X	X.X	X.X	X.X	X.X	X.X
			Maximum	XX	XX	XX	XX	XX	XX
		Change	n	X	X	X	X	X	X
			Mean	X.X^	X.X	X.X	X.X^	X.X	X.X
			SD	X.XX	X.XX	X.XX	X.XX	X.XX	X.XX
			Minimum	XX	XX	XX	XX	XX	XX
			Median	X.X	X.X	X.X	X.X	X.X	X.X
			Maximum	XX	XX	XX	XX	XX	XX

Programmer Note: Means at specific time points will be flagged (with a \*) if they are above or below the reference range. This only applies to the clinical laboratory results (i.e., not the change from baseline or any other endpoints). Time Point column will match those found in Section 8.9 of the SAP.

P1R: < >

P1M: < >

CIG: < >

Baseline is the last measurement collected prior to the first product administration.

# = Lowest of the lower ranges and highest of the higher ranges are used. Refer to Appendix 16.1.10.1 for the breakdown.

\* = Above reference range; ^ = Below reference range

Program: /CAXXXX/sas\_prg/stsas/tab/programname2022Q1.sas DDMMYYYY HH:MM

Philip Morris Products S.A.

THS Induction device and regular or menthol sticks, P1-PK-12

CA39924

Page 1 of X

Table CLBS Clinical Laboratory Shift From Baseline - Serum Chemistry (Safety Population)

Laboratory Test (units)	Randomized Product Sequence	Time Point	Baseline L			Baseline N			Baseline H		
			Post Use			Post Use			Post Use		
			L	N	H	L	N	H	L	N	H
Testname (unit)	XXX	Discharge	X	XX	X	X	XX	X	X	XX	X
	XXX	Discharge	X	XX	X	X	XX	X	X	XX	X
	XXX	Discharge	X	XX	X	X	XX	X	X	XX	X
	XXX	Discharge	X	XX	X	X	XX	X	X	XX	X
	XXX	Discharge	X	XX	X	X	XX	X	X	XX	X
	XXX	Discharge	X	XX	X	X	XX	X	X	XX	X

Programmer Note: For urinalysis, the following footnote is used since the categories of N and O will be used instead of L, N, H:  
 N = Within reference range; O = Outside reference range

P1R: < >

P1M: < >

CIG: < >

Baseline is the last measurement collected prior to the first product administration.

N = Within reference range; L = Below reference range; H = Above reference range

Program: /CAXXXX/sas\_prg/stsas/tab/programname2022Q1.sas DDMMYYYY HH:MM

Philip Morris Products S.A.

THS Induction device and regular or menthol sticks, P1-PK-12

CA39924

Page 1 of X

Table CVS Vital Sign Summary and Change From Baseline (Safety Population)

Vital Sign (units)	Time Point	Statistic	Randomized Product Sequence					
			XXX (N = X)	XXX (N = X)	XXX (N = X)	XXX (N = X)	XXX (N = X)	XXX (N = X)
Testname (unit)	Baseline	n	X	X	X	X	X	X
		Mean	X.X	X.X	X.X	X.X	X.X	X.X
		SD	X.XX	X.XX	X.XX	X.XX	X.XX	X.XX
		Minimum	XX	XX	XX	XX	XX	XX
		Median	X.X	X.X	X.X	X.X	X.X	X.X
		Maximum	XX	XX	XX	XX	XX	XX
Day 2	Absolute	n	X	X	X	X	X	X
		Mean	X.X	X.X	X.X	X.X	X.X	X.X
		SD	X.XX	X.XX	X.XX	X.XX	X.XX	X.XX
		Minimum	XX	XX	XX	XX	XX	XX
		Median	X.X	X.X	X.X	X.X	X.X	X.X
		Maximum	XX	XX	XX	XX	XX	XX
Change	Change	n	X	X	X	X	X	X
		Mean	X.X	X.X	X.X	X.X	X.X	X.X
		SD	X.XX	X.XX	X.XX	X.XX	X.XX	X.XX
		Minimum	XX	XX	XX	XX	XX	XX
		Median	X.X	X.X	X.X	X.X	X.X	X.X
		Maximum	XX	XX	XX	XX	XX	XX

P1R: < >

P1M: < >

CIG: < >

Baseline is the last measurement collected prior to the first product administration.

Program: /CAXXXX/sas\_prg/stsas/tab/programname2022Q1.sas DDMMYYYY HH:MM

Philip Morris Products S.A.

THS Induction device and regular or menthol sticks, P1-PK-12

CA39924

Page 1 of X

Table CEG 12-Lead Electrocardiogram Summary and Change From Baseline (Safety Population)

			Randomized Product Sequence					
Measurement (units)	Time Point	Statistic	XXX (N = X)	XXX (N = X)	XXX (N = X)	XXX (N = X)	XXX (N = X)	XXX (N = X)
Testname (unit)	Baseline	n	X	X	X	X	X	X
		Mean	X.X	X.X	X.X	X.X	X.X	X.X
		SD	X.XX	X.XX	X.XX	X.XX	X.XX	X.XX
		Minimum	XX	XX	XX	XX	XX	XX
		Median	X.X	X.X	X.X	X.X	X.X	X.X
		Maximum	XX	XX	XX	XX	XX	XX
Discharge	Absolute	n	X	X	X	X	X	X
		Mean	X.X	X.X	X.X	X.X	X.X	X.X
		SD	X.XX	X.XX	X.XX	X.XX	X.XX	X.XX
		Minimum	XX	XX	XX	XX	XX	XX
		Median	X.X	X.X	X.X	X.X	X.X	X.X
		Maximum	XX	XX	XX	XX	XX	XX
Change	Change	n	X	X	X	X	X	X
		Mean	X.X	X.X	X.X	X.X	X.X	X.X
		SD	X.XX	X.XX	X.XX	X.XX	X.XX	X.XX
		Minimum	XX	XX	XX	XX	XX	XX
		Median	X.X	X.X	X.X	X.X	X.X	X.X
		Maximum	XX	XX	XX	XX	XX	XX

P1R: < >

P1M: < >

CIG: < >

Baseline is the last measurement collected prior to the first product administration.

Program: /CAXXXX/sas\_prg/stsas/tab/programname2022Q1.sas DDMMYYYY HH:MM

Philip Morris Products S.A.

THS Induction device and regular or menthol sticks, P1-PK-12

CA39924

Page 1 of X

Table CSP Spirometry Summary and Change From Baseline (Safety Population)

			Randomized Product Sequence					
Measurement (units)	Time Point	Statistic	XXX (N = X)	XXX (N = X)	XXX (N = X)	XXX (N = X)	XXX (N = X)	XXX (N = X)
Testname (unit)	Baseline	n	X	X	X	X	X	X
		Mean	X.X	X.X	X.X	X.X	X.X	X.X
		SD	X.XX	X.XX	X.XX	X.XX	X.XX	X.XX
		Minimum	XX	XX	XX	XX	XX	XX
		Median	X.X	X.X	X.X	X.X	X.X	X.X
		Maximum	XX	XX	XX	XX	XX	XX
Discharge	Absolute	n	X	X	X	X	X	X
		Mean	X.X	X.X	X.X	X.X	X.X	X.X
		SD	X.XX	X.XX	X.XX	X.XX	X.XX	X.XX
		Minimum	XX	XX	XX	XX	XX	XX
		Median	X.X	X.X	X.X	X.X	X.X	X.X
		Maximum	XX	XX	XX	XX	XX	XX
Change	Change	n	X	X	X	X	X	X
		Mean	X.X	X.X	X.X	X.X	X.X	X.X
		SD	X.XX	X.XX	X.XX	X.XX	X.XX	X.XX
		Minimum	XX	XX	XX	XX	XX	XX
		Median	X.X	X.X	X.X	X.X	X.X	X.X
		Maximum	XX	XX	XX	XX	XX	XX

P1R: < >

P1M: < >

CIG: < >

Baseline is the last measurement collected prior to the first product administration .

Program: /CAXXXX/sas\_prg/stsas/tab/programname2022Q1.sas DDMMYYYY HH:MM

Philip Morris Products S.A.  
THS Induction device and regular or menthol sticks, P1-PK-12  
[REDACTED] CA39924

---

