7.4.5 Vital Signs

The vital signs (systolic and diastolic blood pressure, respiratory rate, and pulse rate) will be measured as described in the Schedule of Events ([Appendix A](#)). On Day 1 to Day 3, vital signs will be assessed prior to T0.

All parameters will be recorded in supine position after the subject has rested for at least 5 minutes. Subjects should have abstained from using any TNP for at least 15 minutes prior to assessment of vital signs.

The PI will define vital sign ranges to determine normal or abnormal results. For those results outside of the normal range, the PI will determine appropriate follow-up including reporting of any AEs.

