| Time | Procedures | Additional Information |
|-----------------------|---|--|
| Prior to T0 | Vital signs | ≥5 min supine rest |
| Prior to T0 | VAS Craving T _V 0 | ≤15 min prior to T0 |
| ≤5 min prior to T0 | Blood sample T _B 14 | Day 2 sample T _B 13 (24 hrs ±10 min) ≡ T _B 0 of Day 3 |
| Just before T0 | Switch-on of THS (with stick) or lighting of CIG | Performed by investigational site staff |
| T0 | Start of IP use | |
| During / after IP use | Blood sampling (nicotine PK) | Post-T0 time points: T _B 1 after 4 minutes (± 1 min) T _B 2 after 6 min (± 1 min) T _B 3 after 8 min (± 1 min) T _B 4 after 10 min (± 1 min) T _B 5 after 12 min (± 1 min) T _B 6 after 15 min (± 2 min) T _B 7 after 30 min (± 5 min) T _B 8 after 1 hr (± 5 min) T _B 9 after 2 hrs (± 5 min) T _B 10 after 4 hrs (± 5 min) T _B 11 after 10 hrs (± 5 min) |

Confidentiality Statement

Data and information contained in this document are considered to constitute trade secrets and confidential commercial information, and the legal protections provided to such trade secrets and confidential information are hereby claimed under the provisions of applicable law. No part of this document may be publicly disclosed without the written consent of Philip Morris Products S.A.

| | | |
|-------------------------|--|---|
| | VAS Craving | Post-T0 time points Tv1 after 4 min (\pm 2 min) Tv2 after 10 min (\pm 2 min) Tv3 after 15 min (\pm 2 min) Tv4 after 30 min (\pm 2 min) Tv5 after 10 hrs (\pm 5 min) |
| | VAS Liking and VAS Intention to Use Again | Tv3 after 15 min (\pm 1 min) |
| Ongoing | Support during TNP abstinence period | |
| \leq 2 hours after T0 | Breakfast ECG Spirometry Venous blood sample Spot urine sample | \geq 10 min supine rest \geq 15 min sitting rest - Safety panel hematology and clinical chemistry - Safety panel - Pregnancy test (female) |
| \geq 4 hours after T0 | Lunch Vital signs Concomitant disease / concomitant medication AE/SAE recording Product events Information on smoking risks, advice on smoking cessation Discharge | \geq 5 min supine rest Malfunction / misuse Incl. THS briefing Stop of TNP abstinence |

Abbreviations:

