For categorical data, the number and % of subjects with missing data, frequency counts and percentages will be presented.

For PK and PD endpoints, all analyses and summaries will be performed by IP.

For safety endpoints, analyses and summaries will be performed by IP and sequence, and overall.

Post-baseline summaries will include change from baseline apart from log-normal variables which will present % change from baseline.

When applicable, the number and % of subjects with values below the lower limit of quantification (LLOQ) or above the upper limit of quantification (ULOQ) will also be presented. If 50% or more data are below LLOQ or above ULOQ, only the number and percent of values below LLOQ or above ULOQ will be reported in the summaries, together with minimum (= LLOQ/2) and maximum (= ULOQ) of the observed values.

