## 8. SAFETY

All relevant case report form (CRF) data will be listed by subject and chronologically by assessment time point. This will include rechecks, unscheduled, and early termination assessments.

Applicable continuous variables will be summarized using n, mean, SD, minimum, median, and maximum.

The level of precision will be presented as follows: minimum/maximum in the same precision as in the database, mean/median in one more precision level than minimum/maximum, SD in one more precision level than mean/median, and n will be presented as an integer. Percentages will be presented as an integer.

Where individual data points are missing because of dropouts or other reasons, the data will be summarized based on reduced denominators.

Baseline will be the result closest and prior to the product use in the respective period unless otherwise stated. Summaries for post-baseline time points will not include rechecks, unscheduled, or early termination measurements.

Tables summarizing safety data by assessment time point will only include summaries for baseline and post-baseline time points.

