## 8.10 Vital Signs

Vital signs (systolic and diastolic blood pressure, pulse rate, and respiratory rate) will be measured at the Screening Visit, on Admission (Day -1), Preuse on Period 1, Period 2, and Period 3, and Discharge (Period 3) or as early termination assessments, as applicable. All parameters will be recorded in supine position after the subject has rested for at least 5 minutes. Subjects should have abstained from using any TNPs for at least 15 minutes prior to Vital signs assessment.

The Investigator will define vital sign ranges to determine normal or abnormal results. For those results outside of the normal range, the Investigator will determine appropriate follow up including reporting of any AEs.

Descriptive statistics will be reported for vital signs measurements (blood pressure, pulse, respiration, and temperature) by time point. Change from baseline will be summarized in a similar manner. Baseline is defined as the result closest and prior to the first product administration, which may include unscheduled or recheck results. This will typically be the result collected on prior to T0 on Day 1. Post product use unscheduled events or rechecks

Philip Morris Products S.A.  
THS Induction device and regular or menthol sticks, P1-PK-12  
[REDACTED] CA39924

---

will not be included in summaries. Similarly, early termination results will not be included in summaries.

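### Vital-sign changes are all taken from one value before the first product and tabulated by sequence only, so the Day 2 and Day 3 pre-use readings never serve as the comparator for their own period

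*SAP*

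**What the plan says.** SAP 8 gives a general rule for safety data: "Baseline will be the result closest and prior to the product use in the respective period unless otherwise stated". SAP 8.10 then sets a different rule for vital signs: "Baseline is defined as the result closest and prior to the first product administration, which may include unscheduled or recheck results". It adds: "This will typically be the result collected on prior to T0 on Day 1". The footnote of shell CVS in SAP 12.3 repeats the single baseline: "Baseline is the last measurement collected prior to the first product administration". The columns of CVS are the six randomized sequences, and there is no product column. The shell prints only the Baseline and Day 2 rows; the Day 3 and Discharge rows follow from the time points listed in SAP 8.10.

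The readings for a period-specific change are planned. Protocol 7.4.5 states: "On Day 1 to Day 3, vital signs will be assessed prior to T0". Table 7 in Protocol 9.5 adds a second Day 3 reading, in the row for at least 4 hours after T0, together with lunch and the discharge procedures.

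On display, Protocol 12.1.2 says: "For safety endpoints, analyses and summaries will be performed by IP and sequence, and overall". Protocol 12.5.2 asks for vital signs by study day and says that safety variables from the exposure periods will also be reported by sequence. SAP 9 declares no difference from the protocol's planned analyses.

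**The concern.** Change in vital signs from baseline is a named endpoint under the secondary objective on the safety of the test products. In a three-period crossover, a reader expects such a change to be readable product by product. With one baseline before the first product, only the Day 2 change follows a single use. The Day 3 pre-use change follows two, and the Discharge change follows three. Adding a product column to the table as it stands would not be enough, because most of the changes in it follow more than one product.

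The Discharge reading matters most. It is the only scheduled vital-sign reading taken on the same day after a use, so it is the one most likely to carry some product effect. The plan compares it with a value from two days and two products earlier, although a pre-use value from that same morning exists.

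ECG, spirometry and the laboratory panel have no reading between products, so a single baseline is unavoidable for them. For vital signs it is a choice, and the SAP gives no reason for it.

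**Working it through.** The documents give no figure on this point, so the check is a count.

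**Inputs**
- 30 subjects and 6 sequences (SAP 3), so 30/6 = 5 per sequence.
- Four scheduled readings from Day 1 on: pre-use on Days 1, 2 and 3, and Discharge on Day 3 (SAP 8.10; Protocol 7.4.5 and Table 7).
- Baseline: the last value before the first product, taken here as Day 1 pre-use.
- Nicotine half-life of about 2 hours (Protocol 12.1.2).

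**Product uses between comparator and reading** (the same in all six sequences)

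| Reading | From the SAP 8.10 baseline | From the preceding pre-use reading |
|---|---|---|
| Day 2 pre-use | 1 | 1 |
| Day 3 pre-use | 2 | 1 |
| Discharge | 3 | 1 |

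**By sequence.** There are 6 × 3 = 18 sequence-by-time changes. Under SAP 8.10, 6 of 18 follow one use. With a period-specific baseline, 18 of 18 do.

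**By subject, assuming 30 completers.** There are 30 × 3 = 90 changes. Under SAP 8.10, 30 follow one use and 2 × 30 = 60 follow two or three (60/90 = 67%). The 30 single-use changes all come from Period 1, 30/3 = 10 per product. With a period-specific baseline, all 90 follow one use: 10 per product in each of three periods, 30 per product in total. Each product comes last in 2 of the 6 sequences, so the Discharge change rests on 2 × 5 = 10 subjects per product.

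**What could still be acting at each reading.** The remaining fraction of nicotine after h hours is 0.5^(h/2).
- 23 hours: 0.5^11.5 = 0.035%, within the protocol's own ceiling of 0.05%.
- 24 hours (Day 2 and Day 3 pre-use): 0.5^12 = 0.024%.
- 4 hours (the earliest time that Table 7 allows for Discharge): 0.5^2 = 25%.
- 10 hours (the time of the last Day 3 blood sample): 0.5^5 = 3.1%.

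So the gain from a same-period comparator lies mainly at Discharge.

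**Can the planned table be unpicked?** In part. If the same subjects contribute at both times, mean(Day 3 − Day 1) minus mean(Day 2 − Day 1) equals mean(Day 3 − Day 2). The SD does not follow, because Var(Day 3 − Day 2) = Var(Day 3 − Day 1) + Var(Day 2 − Day 1) − 2 Cov, and the covariance is not tabulated. The median, minimum and maximum do not follow either.

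**The case against.** The strongest case for the plan is that a single pre-exposure baseline is a legitimate safety choice and was made openly. SAP 8 yields where a later section states otherwise, and 8.10 does so. A reader might infer that the SAP contradicts itself on baseline; it does not. Protocol 12.1.2 fixes a per-day baseline for PK and PD only, and CVS supplies the study-day and sequence displays that Protocol 12.5.2 describes. All of that stands. What it leaves open is the by-product summary in Protocol 12.1.2, which CVS does not give.

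A reader might also infer that 60 of the 90 changes are contaminated by a mixture of product effects. The documents do not support that. The Day 2 and Day 3 pre-use readings come at least 24 hours after the last use, when almost no nicotine remains. The 67% counts exposures, not carried-over effect. For the same reason, a period-specific change for Periods 1 and 2 is mostly one day's variation, and printing it under a product name could be over-read. No baseline rule cures the lack of same-day post-use readings in those periods.

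Nor does the change from baseline capture the switch from usual smoking to confinement. By the typical baseline, subjects have been admitted and have abstained for at least 23 hours.

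Discharge minus that morning's value mixes product with time of day and meals. That is true, but the Day 1 baseline is also a morning value, so the planned change has the same problem.

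Finally, it would be too strong to say that the planned changes can never be traced to one product. The sequence columns show product order, period means can be recovered from complete data, and Appendix 16.2.8.7 lists the readings. A listing, however, does not replace a summary.

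**Conclusion.** The point holds as a limited analysis choice worth improving. Under SAP 8.10 and CVS, 60 of 90 planned vital-sign changes follow two or three uses, the table has no product column, and the one same-day post-use reading lacks its same-day comparator, although the data for all three are already collected. The count assumes 30 completers, equal allocation to sequences, and Day 1 pre-use as the baseline. SAP 8.10 calls that typical and allows an unscheduled or recheck value, but any value before the first product gives the same count.

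The consequence is modest. The study tests no hypothesis, the endpoint is secondary and descriptive, and no PK result depends on it. The documents give no variability for vital signs, so the size of any effect on the reported changes cannot be stated.

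**What to change.** In SAP 8.10 and shell CVS, add a by-product, period-specific change:
- Discharge minus Day 3 pre-use, for the Period 3 product, as its own row.
- Day 2 pre-use minus Day 1 pre-use, for the Period 1 product.
- Day 3 pre-use minus Day 2 pre-use, for the Period 2 product.

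Keep the change from Day 1 by sequence and study day, so that nothing now planned is lost.

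Add two footnotes. The first should say that the Period 1 and 2 changes are read about 24 hours after use, so they reflect mainly day-to-day variation and not acute product effect. The second should say that the Discharge change also includes time of day and meals and rests on about 10 subjects per product.

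The cost is a change of SAP wording and one derived variable, with no new measurement and no new subject. The downsides are a longer table and the risk that the 24-hour changes are over-read, which the first footnote is there to limit.
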